7.5 Adjustments for Multiple Comparisons

No adjustments will be made.

7.6 Demographic and Other Baseline Characteristics

Subject characteristics, including age, gender, ethnicity, diabetes History, height, weight, BMI and baseline HbA1C will be summarized by descriptive statistics (mean, standard deviation, minimum, median, and maximum) for continuous variables and by counts and percentages for categorical variables.

7.7 Health Outcomes Analyses

Descriptive summary will be used to characterize data from questionnaires that are given to subjects to record feedback.

7.8 Commercial Data Evaluation: Carelink Database Analysis

Analysis from the Carelink database with patients on the MiniMed 530G system intends to provide a large heterogeneous source of data taken from the actual commercial use with MiniMed 530G. The focus of this analysis is to provide a robust data set on the safety of this system. To this end, our analysis will not only provide a summary of glucose control and correlation with the use of the Threshold Suspend (TS) feature but will provide a focused analysis on key aspects of the MiniMed 530G system as it relates to the safety of the system.

Datasets will come from MiniMed 530G patients and insulin pumps sold and uploaded within date windows.

7.8.1 Primary Safety Endpoint

The difference in self-reported first A1C and subsequent A1C collected from StartRight program. The mean difference in A1C will be estimated and compared by a non-inferiority test with a significance level of 0.025 (one-sided).

The overall difference in A1C will be estimated and compared by a non-inferiority test with an A1C margin of 0.4% and a significance level of 0.025 (one-sided). The null hypothesis will be rejected if the one-sided 97.5% upper confidence limit of the mean difference in A1C is less than 0.4%

The hypothesis is mathematically expressed as:

Ho: $\mu \geq 0.4\%$

Ha: $\mu < 0.4\%$

Where 0.4% is the pre-specified non-inferiority margin, μ is the mean of difference in A1C (%).

Primary safety endpoint will be presented and tested using pair t-test on those subjects with both first and subsequent A1c.

Descriptive subgroup analysis of A1c data will be performed on demographic cohorts (age, gender, duration of diabetes and years on insulin), and first A1c (less than 7.0%, 7.0-9.0%, greater than 9.0%)

This analysis addresses the primary and secondary safety endpoint per conditions of approval in FDA 530G approval letter

7.8.2 Primary Efficacy Endpoint

Two primary efficacy endpoints are defined below. The study will be considered successful if both endpoints are met. Therefore, alpha is kept at a significance level of 0.025 (one sided).

Primary efficacy endpoint will be presented and tested using pair t-test on those subjects with both TS feature ON and TS feature OFF within date windows.

7.8.2.1 Co-Primary Efficacy Endpoint:

The difference in percent time spent <70 mg/dL using sensor glucose values from TS feature ON and TS feature OFF. The mean change in percent time spent <70 mg/dL (TS feature ON and TS feature OFF) will

be estimated and compared by a superiority test with a significance level of 0.025 (one-sided). The goal is to show superiority of the TS feature ON compared to the TS feature OFF.

The hypothesis is mathematically expressed as:

$$H_0: \mu_{\text{TS Feature ON}} \geq \mu_{\text{TS Feature OFF}}$$

$$H_a: \mu_{\text{TS Feature ON}} < \mu_{\text{TS Feature OFF}}$$

where μ (TS feature ON) is the subject mean of percent time with SG below 70 mg/dL during TS feature ON, μ (TS feature OFF) is the subject mean of percent time with SG below 70 mg/dL during TS feature OFF.

7.8.2.2 Co-Primary Efficacy Endpoint:

The difference in percent time spent >180 mg/dL using sensor glucose values from TS feature ON and TS feature OFF. The mean change in percent time spent >180 mg/dL (TS feature ON and TS feature OFF) will be estimated and compared by a non-inferiority test with a significance level of 0.025 (one-sided) and a margin of 5%. The goal is to show non-inferiority of the TS feature ON compared to the TS feature OFF.

The hypothesis is mathematically expressed as:

$$H_0: \mu_{\text{TS Feature ON}} \geq \mu_{\text{TS Feature OFF}} + 5\%$$

$$H_a: \mu_{\text{TS Feature ON}} < \mu_{\text{TS Feature OFF}} + 5\%$$

where μ (TS feature ON) is the subject mean of percent time with SG > 180 mg/dL during TS feature ON, μ (TS feature OFF) is the subject mean of percent time with SG > 180 mg/dL during TS feature OFF.

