## 6. Study Population of Multi-Center Trial

### 6.1. Number of Subjects and CEP266 Study Population

A total of 426 subjects have been enrolled in the study.

40 Investigational centers were activated across the United States. Selection was based on Investigator's experience and qualifications, availability of sufficient resources to carry out the required study procedures and the investigator's ability to recruit subjects into the study.

Subjects will be grouped by baseline demographics: Baseline A1C, age, race, ethnicity, body mass index (BMI), gender, diabetes classification, duration of diabetes, hypoglycemic awareness and transition group. Sponsor will oversee distribution of subjects across study sites.

Summary of data will include the following baseline demographic categories:

- **Baseline A1C**
  - A1C less than 7.0%
  - A1C between 7.0% to 9.0%
  - A1C greater than 9.0%
- **Age Groups**
  - Adults age 22-and older
  - Adolescents age 16-21
- **Ethnicity**
  - Hispanic/Latino
  - Non-Hispanic/Non-Latino
  - Subject refused
- **Race**
  - American Indian/Alaska Native
  - Black/African-American

- White - anticipated maximum less than 80%
- Native Hawaiian/Other Pacific Islander
- Asian
- Other
- Subject refused
- **BMI according to WHO criteria [World Health Organization, 2011]:**
  - Underweight subjects (BMI less than 18.5 kg/m^2)
  - Normal weight subjects (BMI 18.5 to 24.99 kg/m^2)
  - Overweight subjects (BMI 25.00 to 29.99 kg/m^2)
  - Obese subjects (BMI 30.00 to 39.99 kg/m^2)
  - Morbidly obese subjects (BMI greater than or equal to 40 kg/m^2)
- **Gender**
  - Male
  - Female
- **Diabetes Classification**
  - Diabetes type 1
  - Diabetes type 2
  - Other diagnosis of Diabetes
- **Duration of diabetes**
  - Duration of diabetes less than 20 years
  - Duration of diabetes greater than or equal to 20 years
- **Hypoglycemic awareness**
  - Patients with intact hypoglycemic awareness
  - Patients who have impaired hypoglycemic awareness

- **Transition Groups**

The “transition” to the 530G system is based on the first time the TS (threshold suspend) feature is turned ON, outside/excluding pump training.

- Naïve: Subjects who have been exposed to the 530G pump therapy with the TS feature ON for 7 days or less prior to screening.
- Non-Naïve: Subjects who have been exposed to the 530G pump therapy with the TS feature ON for 8 to 365 days prior to screening.

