## 7.2.2. Primary Efficacy Endpoint

Two primary efficacy endpoints are defined below (see sections 7.2.2.1 and 7.2.2.2). The study will be considered successful if both endpoints are met. Therefore alpha is kept at a significance level of 0.025 (one sided).

Primary efficacy endpoint will be presented and tested using pair t-test on those subjects with both TS feature ON and TS feature OFF within date windows.

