7.8.6.2 Sample Size for Co-Primary Efficacy Endpoint

The difference in percent time spent <70 mg/dL using sensor glucose values from TS feature ON and TS feature OFF. The mean difference in percent time spent <70 mg/dL (TS feature ON and TS feature OFF) will be estimated and compared by a superiority test with a significance level of 0.025 (one-sided). The goal is to show superiority of the TS feature ON compared to the TS feature OFF.

The hypothesis is mathematically expressed as:

H0: $\mu_{\text{TS Feature ON}} \geq \mu_{\text{TS Feature OFF}}$

Ha: $\mu_{\text{TS Feature ON}} < \mu_{\text{TS Feature OFF}}$

Sample size estimates for time in hypoglycemic range is based on paired t test with a one-sided type I error rate of 2.5%. Assume in TS feature ON, the mean is 5% with standard deviation of 4%, In TS feature OFF, mean is 9% with standard deviation of 6%, SAS power and sample size calculator shows that a total of 200 subjects will provide over 90% power to detect the superiority of TS feature ON compared to TS feature OFF.

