7.8.6.3 Sample Size for Co-Primary Efficacy Endpoint

The difference in percent time spent >180 mg/dL using sensor glucose values from TS feature ON and TS feature OFF. The mean difference in percent time spent >180 mg/dL (TS feature ON and TS feature OFF) will be estimated and compared by a non-inferiority test with a significance level of 0.025 (one-sided) and a margin of 5%. The goal is to show non-inferiority of the TS feature ON compared to the TS feature OFF.

The hypothesis is mathematically expressed as:

H0: $\mu_{\text{TS Feature ON}} \geq \mu_{\text{TS Feature OFF}} + 5\%$

Ha: $\mu_{\text{TS Feature ON}} < \mu_{\text{TS Feature OFF}} + 5\%$

Sample size estimates for time in hyperglycemic range is based on paired t test with a one-sided type I error rate of 2.5%. Assume in TS feature ON, the mean is 21% with standard deviation of 9%, In TS feature OFF, mean is 25% with standard deviation of 10%, SAS power and sample size calculator shows that a total of 200 subjects will provide over 90% power to detect the non-inferiority of TS feature ON compared to TS feature OFF, with a margin of 5%.

8 Validation Requirements

Level I or Level II validation are required for analysis output. Level I requires that the peer reviewer independently programs output and then compares the output with that generated by the original Statistical Programmer. Level II requires that the peer reviewer reviews the code; where appropriate, performs manual calculations or simple programming checks to verify the output.

9 References

3. Streja D. Can continuous glucose monitoring provide objective documentation of hypoglycemia unawareness? *Endocr Pract.* 2005;11(2):83-90.
4. Juvenile Diabetes Research Foundation, Continuous Glucose Monitoring Study Group. The Effect of Continuous Glucose Monitoring in Well-Controlled Type 1 Diabetes. *Diabetes Care*, Volume 32, Number 8, August 2009: 1378-1383

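### The commercial TS ON versus OFF tests ignore time on the 530G and ON/OFF order, so change within users over time biases the TS effect in a direction the planned output cannot show

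*SAP*

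**What the plan says.** SAP 7.8.2 and Protocol 7.2.2 set two co-primary efficacy endpoints for the commercial CareLink data. One is superiority of TS ON over TS OFF on percent time below 70 mg/dL. The other is non-inferiority on percent time above 180 mg/dL with a 5-point margin. Both must be met, and the SAP adds: "Therefore, alpha is kept at a significance level of 0.025 (one sided").

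The quantity compared is one value per user and state. For the first endpoint, the ON value "is the subject mean of percent time with SG below 70 mg/dL during TS feature ON", with a matching OFF value. The SAP has the endpoints "tested using pair t-test on those subjects with both TS feature ON and TS feature OFF within date windows", and Protocol 7.2.2 says the same.

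Neither section names a term for calendar time, time since starting the 530G, or order of the two states. Neither sets a minimum ON or OFF exposure or matches the two in time. Date windows are mentioned in SAP 7.8 and Protocol 7.2, but no dates are given.

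The only sensitivity analysis (SAP 7.2.1.1) and the only model with time terms (SAP 7.2.1) belong to the multi-center A1C endpoint. The utilization cohorts in SAP 7.8.3 are descriptive.

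**The concern.** A paired t-test removes stable differences between users. It does not remove change within a user between the OFF weeks and the ON weeks. In a randomised crossover, balanced order deals with that. Here the data are commercial uploads and the user decides when TS is on, so nothing in the design balances order.

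Some change over time is plausible on the plan's own account. SAP 7.8.3.1 links higher sensor use to better glucose control and notes that wear may change with insurance or finances.

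The sub-study's efficacy claim rests on these two tests. A general improvement that coincides with later ON use could look like superiority below 70 mg/dL, or could hide a real rise above 180 mg/dL. In the opposite order it would count against TS. As planned, the report would not let a reader tell which case applies.

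**Working it through.** **Inputs from the plan (SAP 7.8.6.2 and 7.8.6.3).** n=200, one-sided alpha 0.025. Below 70 mg/dL: "Assume in TS feature ON, the mean is 5% with standard deviation of 4"%, and "In TS feature OFF, mean is 9% with standard deviation of 6"%. Above 180 mg/dL: ON mean 21%, SD 9%; OFF mean 25%, SD 10%; margin 5 points.

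**Assumed, because the documents are silent.** Within-user correlation rho (0.5, range 0 to 0.8 unless stated), fall D from a user's earlier to later period, and share q of users whose OFF data come first.

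**1. The plan's own figure.** SD of the difference = √(s₁² + s₂² − 2·rho·s₁·s₂). At rho 0.5:
- Below 70: √(16+36−24) = 5.29, SE = 5.29/√200 = 0.374.
- Above 180: √(81+100−90) = 9.54, SE = 9.54/√200 = 0.675.

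The planned distances are 4 points, and 5+4 = 9 points from the margin. Power at n=200 exceeds 99.9% for both at every rho from −0.5 to 0.75, so the stated figure of over 90% holds. About 11 to 50 and 6 to 36 users would give 90%. Sample size is not the problem.

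**2. The bias.** Let tau be the true ON minus OFF effect. An OFF-first user has expected difference tau − D and an ON-first user tau + D. The average is tau − D(2q−1). The t-test estimates this, not tau.

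**3. Illustration at q=0.75, so 2q−1 = 0.5.** By the normal approximation, false-positive rate = Φ(bias/SE − 1.96).

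| Endpoint and truth | D | Bias | Rate, rho 0.5 | rho 0 to 0.8 |
|---|---|---|---|---|
| <70, no TS effect | 0.5 | 0.25 | Φ(0.668−1.96) ≈ 10% | 7% to 16% |
| >180, true rise of 5 | 1 | 0.50 | Φ(0.741−1.96) ≈ 11% | 8% to 21% |

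Simulation gave the same values. With no drift the rate was 2.3% to 2.7%.

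**4. Other orders.** At q=0.5 the bias is zero, and the simulated rate was 2.2% to 2.7% for D from 0 to 2. At q=0.25 with D=0.5 the bias is 0.25 against TS. False superiority then falls to Φ(−0.668−1.96) ≈ 0.4%, and power for a true 1-point benefit drops from Φ(2.67−1.96) ≈ 76% to Φ(0.75/0.374−1.96) ≈ 52%.

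**5. A larger database.** A net bias of 0.25 point below 70 mg/dL (rho 0.5) gives false superiority of 32% at n=1,000 and 92% at n=5,000. More users tighten the interval around the biased value.

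**6. What an order term does.** Regressing the paired difference on order (±1) at q=0.75 and rho 0.5 returned the two rates in step 3 to 2.6% and 2.3%. At q=0.8 and D=1 (below 70), error was 36% unadjusted and 2.5% adjusted. The data were generated under that same order model, so this shows that the term works when its form is right.

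**7. What it costs.** Variance inflation = 1/(1−(2q−1)²): 1.33 at 75/25 and 1/(1−0.64) = 2.78 at 90/10. Power at the planned effects stays above 99%. For a true 1-point effect below 70 it falls from 76% to about 64% at 75/25 and 36% at 90/10.

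**The case against.** The strongest reply is that nothing shows OFF data coming first in commercial users. A reader might infer it from Protocol 6.1, where transition "is based on the first time the TS (threshold suspend) feature is turned ON", or from Protocol 11.2.1, which tells naïve subjects to leave TS off until Baseline. Both concern subjects of the multi-center trial and say nothing about order among CareLink users. This stands: the direction of any bias is unknown.

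A reader might also take the planning values above 180 mg/dL ("In TS feature OFF, mean is 25% with standard deviation of 10"%, against 21% ON) as a sign of built-in drift, since suspending insulin does not directly lower high glucose. The documents do not support that. The figures have no stated source, TS could act indirectly through behaviour, and drift over months is only one of several possible explanations.

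Larger error rates appear if every user is assumed OFF-first: 26% and 31% for the two cases in step 3. No document supports that assumption, and an order term could not be estimated under it.

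Two further points stand in part. The commercial data support the multi-center trial, whose A1C endpoint does not use these tests, so replacing the primary test is not the only reasonable answer. And both tests must pass, so each rate above is an upper limit on a false joint claim arising from that endpoint, reached only when the other test is almost sure to pass.

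The SAP pages after the references are not readable in the available copy, so their content is unknown.

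**Conclusion.** The point holds in a conditional form. In every readable section, both co-primary tests reduce each user to one ON and one OFF mean, with no adjustment for time or order, undefined date windows and no sensitivity analysis. Any shared change over time then enters the TS effect by the factor (2q−1). That factor follows from the planned test and needs no assumption about which state comes first.

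The size does rest on assumptions. About 10% and 11% against 2.5% require 75% OFF-first, correlation 0.5 and falls of 0.5 and 1 point. They show that a drift well below the planned 4-point effect could matter. They are not estimates for this database. The documents do not support a claim that the result will favour TS. They do show that the planned output could not rule out bias in either direction. The change should be made, because the pump and sensor uploads needed for it are already part of the data set.

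**What to change.** In SAP 7.8.2 and Protocol 7.2.2:

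1. State the date windows.
2. Report the number of OFF-first and ON-first users, the timing of their ON and OFF data, and the ON minus OFF difference in each order group.
3. Prespecify, at least as a key sensitivity analysis for both co-primary endpoints, a within-user, time-adjusted comparison in users with both states. Either of two forms would do:
   - pairs built from ON and OFF data in the same or adjacent weeks, with an order term; or
   - a weekly model with fixed user effects (or TS centred within user), time since first 530G upload, and standard errors clustered by user. A plain random user effect is not enough, because it lets differences between users into the TS coefficient, which the paired test keeps out.
4. Say that the success claim will be limited if adjusted and unadjusted results disagree. If nearly all users share one order with no overlap in time, say that TS cannot be separated from time on the device.

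The present paired t-test can stay. The cost is wording, programming, a wider interval and less information from users whose ON and OFF data do not overlap. The precision figures in the working apply to the order term only. The weekly model was not simulated, so its power should be checked before it is adopted.

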7.8.3 Descriptive Endpoint

- Adverse Events collected via Outreach program. Adverse events (Hospitalized High BG and Hospitalized Low BG) collected during Outreach program will be summarized and presented. Adverse event rates in 100 patient years will also be reported. Adverse events will be further stratified by device component (pump, sensor, sensor server, infusion set, infusion set server, reservoir or accessories), age, gender duration of diabetes and years on insulin.
- The difference in estimated A1C ((average sensor glucose + 36.9) / 28.0) from TS feature ON and TS feature OFF [Nathan D, etc. 2008]. Subgroup analysis of A1c data will be performed on demographic cohorts (age, gender, duration of diabetes and years on insulin), and first A1c (less than 7.0%, 7.0-9.0%, greater than 9.0%). This analysis addresses the primary and secondary safety endpoint per conditions of approval in FDA 530G approval letter
- TS Feature Utilization: TS feature utilization will be calculated using the available SG with TS feature 'turned on', divided by the period of MiniMed 530G device use (i.e. 288 * Number of days with TDD > 0 units) * 100.

Validation of correct TS feature activation (i.e., insulin suspension) with fingerstick when available will be provided including:

1. Total number of insulin suspensions from TS feature activations
2. Total number of insulin suspensions which were accompanied by fingerstick glucose. (fingerstick glucose needs to be within 30 minutes from the Threshold Suspend activation or while the TS is active)

3. Total number of insulin suspensions with fingerstick glucose, categorized by three groups: 1) within $\pm 20\%$, 2) above 20% and 3) below 20% from the sensor glucose value. If SMBG is less than 75 mg/dl, 15 mg/dl will be used to determine which group it belongs to.
- Hypoglycemic Event Incidence, duration and percentage of time spent (SG less than or equal to 50 and 70 mg/dL): with and without TS feature ON, with or without fingerstick glucose. A hypoglycemic event is defined by SG less than the defined threshold for at least 20 minutes. Validation of CGM with fingerstick when available will be provided including:
 1. Total number of hypoglycemic events
 2. Total number of hypoglycemic events that were accompanied by fingerstick glucose (fingerstick glucose needs to be within 30 minutes from the Threshold Suspend activation or while the TS is active)
 3. Total number of hypoglycemic event with fingerstick glucose, categorized by three groups: 1) within $\pm 20\%$, 2) above 20% and 3) below 20% from the sensor glucose value. If SMBG is less than 75 mg/dl, 15 mg/dl will be used to determine which group it belongs to.
 - Hyperglycemic Event Incidence, duration and percentage of time spent (SG greater than or equal to 180, 250, 300, and 400 mg/dL) with and without TS feature ON; with fingerstick or not. A hyperglycemic event is defined by SG greater than the defined threshold for at least 20 minutes. Provision of fingerstick data when available will provide a separate and important reference to CGM data. Validation of CGM with fingerstick when available will be provided including:
 1. Total number of hyperglycemic events
 2. Total number of hyperglycemic events that were accompanied by fingerstick glucose (fingerstick glucose needs to be within 30 minutes from the Threshold Suspend activation or while the TS is active)
 3. Total number of hyperglycemic event with fingerstick glucose, categorized by three groups: 1) within $\pm 20\%$, 2) above 20% and 3) below 20% from the sensor glucose value. If SMBG is less than 75 mg/dl, 15 mg/dl will be used to determine which group it belongs to.
 - Characteristics of patient behavior for each cohort (e.g. Cohort 1-5 below) will be provided. The provision of this data will help to better understand the profile of patients using this device.

Cohort Description:

- Cohort 1: 0-24% TS feature utilization
- Cohort 2: 25-49% TS feature utilization
- Cohort 3: 50-74% TS feature utilization
- Cohort 4: 75-100% TS feature utilization
- Cohort 5: Data from all 530G uploads regardless of TS feature utilization

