## 2. Devices and Supplies

### 2.1. Names and Intended Use of Devices

#### 2.1.1. Medtronic MiniMed® 530G Pump (MMT-551, MMT-751) – FDA approval P120010

The Medtronic MiniMed® 530G Pump model (MMT-551, MMT-751) used in this study is an approved device in the United States. This insulin pump is equipped with a number of features to actively manage the user's glucose levels. The Threshold Suspend (TS) feature automatically stops insulin delivery based on a low Sensor Glucose Value (SGV). The TS feature is only available when the pump is used in conjunction with continuous glucose monitoring (CGM) which consists of a subcutaneous glucose sensor and transmitter to communicate sensor glucose readings to the insulin pump. Threshold Suspend is the first feature available using Medtronic SmartGuard™ technology. SmartGuard refers to all automated insulin delivery and suspension actions by Medtronic sensor-integrated insulin pump systems.

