#### **14.1.5. Potential risks specific to TS Feature:**

- When TS is turned ON, the feature may not activate when the blood sugar is low.
- When TS is turned ON, the feature may falsely activate when the subject's blood sugar is not low.
- The TS feature is not intended to prevent or treat hypoglycemia.

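### The table meant to validate TS suspensions measures fingerstick–sensor agreement and does not show whether glucose was low

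*SAP*

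**What the plan says.** SAP 7.8.3 (same text in Protocol 7.2.3) opens the item with "Validation of correct TS feature activation (i.e., insulin suspension) with fingerstick when available will be provided including". Three counts follow: all suspensions, those with a fingerstick, and "Total number of insulin suspensions with fingerstick glucose, categorized by three groups". The groups are defined by distance from the sensor value: within ±20%, more than 20% above, more than 20% below. A tolerance switch is added: "If SMBG is less than 75 mg/dl, 15 mg/dl will be used to determine which group it belongs to". On timing, the "fingerstick glucose needs to be within 30 minutes from the Threshold Suspend activation or while the TS is active".

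The same three groups are reused in that section for hypoglycemic and hyperglycemic events. There they are introduced as validation of the CGM, not of the activation.

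Protocol 14.1.5 lists among the TS-specific risks that "the feature may falsely activate when the subject's blood sugar is not low".

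**The concern.** The item's title promises evidence on whether the suspension was correct, but the classification never compares the fingerstick with a low-glucose cut-off or with the user's TS threshold. The 75 mg/dL figure only switches the tolerance. Because TS acts on sensor glucose, the fingerstick is the independent evidence on the risk named in Protocol 14.1.5, and the table does not use it for that.

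The study objective (SAP section 4) is to show that home use of TS is not associated with glycemic deterioration, and SAP 7.8 says the commercial analysis focuses on safety. Stopping insulin when glucose is not low is one route to deterioration. As written, the report could not say how often this happened among fingerstick-checked suspensions, and a reader could take the *within* count as the answer.

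**Working it through.** The plan gives no sample size, expected rate or other figure for this item, so there is nothing to reproduce. The check applies the printed rule to specific values.

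**Inputs.** The tolerance is 15 mg/dL if SMBG < 75, otherwise 20% (SAP 7.8.3). The base is taken as SG, because the groups are stated relative to the sensor value. The low cut-off is 70 mg/dL, from the same section: "Hypoglycemic Event Incidence, duration and percentage of time spent (SG less than or equal to 50 and 70 mg/dL". Applying that sensor cut-off to a fingerstick is an assumption. Sensor values of 40, 50, 60, 65 and 70 are the low-glucose cut-offs in SAP 7.2.4.2; the documents give no numeric range for the TS setting.

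**Rule.** d = SMBG − SG. The pair is *within* if |d| ≤ tolerance, *above* if d > tolerance, *below* if d < −tolerance.

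**Worked pairs.**

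| SG | SMBG | d | Tolerance | Group | Low (≤70)? |
|---|---|---|---|---|---|
| 60 | 74 | +14 | 15 | within | no |
| 70 | 84 | +14 | 0.20 × 70 = 14 | within | no |
| 70 | 54 | −16 | 15 | below | yes |
| 50 | 66 | +16 | 15 | above | yes |

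**Full ranges (whole mg/dL).**

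| SG | *Within* spans SMBG | Not low but *within* | Low but outside *within* |
|---|---|---|---|
| 40 | 25–55 | none | <25; 56–70 |
| 50 | 35–65 | none | <35; 66–70 |
| 60 | 45–74 | 71–74 | <45 |
| 65 | 50–78 | 71–78 | <50 |
| 70 | 55–84 | 71–84 | <55 |

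The not-low-but-*within* case therefore needs a sensor value above about 55 mg/dL (SG + 15 > 70). The low-but-*above* case arises only at the lower sensor values.

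**Two gaps in the rule.**
- Base of the 20%: if it is taken of SMBG, *within* ends at 75, 81 and 87 for SG 60, 65 and 70, instead of 74, 78 and 84.
- Paired sensor value: the plan does not say whether this is the value at activation or at the time of the fingerstick. With the latter, SG 110 and SMBG 120 late in a suspension is *within* (d = 10, tolerance 0.20 × 110 = 22).

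**Illustrative size only.** Suppose SMBG is normal around SG, with bias 0 or +10 and SD 10 to 20 mg/dL; none of this comes from the documents. The share of *within* pairs with SMBG > 70 is then about 10–28% at SG 60 and 49–77% at SG 70. The share of low pairs falling outside *within* is about 1–33% at SG 60 and 4–45% at SG 70. The width of these ranges shows that the documents cannot settle the size.

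**The case against.** **The plan never calls *within* correct.** It gives counts in three directional groups, and *above* is shown separately, so large discrepancies are visible. This stands: the table is not silent on the risk. But *above* can include fingersticks that are still low (SG 50, SMBG 66), and *within* can include some that are not, so neither count answers the question in the title.

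**Agreement is a proper measure for a device that acts on sensor glucose.** This stands, and is why the table should be kept. The mismatch lies in what it is said to validate.

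**The consequences are measured elsewhere.** A1C, time above 180 mg/dL, hospitalisations for high glucose and, in the trial, hyperglycemic events within 4 hours of TS activation are all planned. This stands: no hypothesis test depends on this table. But none of these items states a comparison of suspensions with a fingerstick against a low cut-off. The trial's CGM-versus-meter item is unspecified. SAP pages 20 to 52 have no readable text in the copy reviewed, so any table layouts there should be checked.

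**A reader might infer that most of the *within* group were wrong suspensions.** One simulation gives 51–65% of that group above the user's threshold, and 36–78% of above-threshold suspensions landing in *within*. It assumes lognormal glucose (mean 150, SD 60 mg/dL), relative sensor error SD 12–20% and thresholds 60–90. The documents do not support that reading: they give no sensor error for this purpose and no threshold of 80 or 90, and Protocol 14.1.5 speaks of glucose that is not low, not of glucose above the setting. Under the same assumptions the median excess over threshold in that group is only 5–7 mg/dL, and at a threshold of 60 only 10–15% of the group exceeds 70.

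**A reader might also infer that correct suspensions are often scored as disagreement.** In that simulation *below* holds only 0–5% of suspensions. That all of them were at or below threshold is true by construction: SG is at or under the threshold and SMBG is under SG.

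**Conclusion.** The point holds as a mismatch between label and measure. The item titled as validating correct activation reports sensor agreement, and agreement can differ from low/not-low status in both directions. This follows from the printed rule and the plan's own 70 mg/dL cut-off, assuming that cut-off may be applied to a fingerstick. How many suspensions are affected cannot be computed from the documents.

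It is a reporting weakness in a descriptive endpoint with no pass/fail rule, and no primary conclusion changes. It is still worth correcting, because the fingersticks are already in the analysis and bear directly on a risk the protocol names.

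A reader might go on to call every suspension with glucose above the threshold false. That would mislead: in the simulation described above, sensor error of only 5% puts 38–39% of suspensions above the threshold, and 2% puts 15–19% there.

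**What to change.** In SAP 7.8.3 and Protocol 7.2.3:

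1. Relabel the three-group table as fingerstick–sensor agreement. State which sensor value is paired (at activation or at the time of the fingerstick) and whether the 20% is of SG or SMBG.
2. Add a table that classifies the fingerstick nearest to activation, inside the plan's 30-minute window, as ≤70 or >70 mg/dL. State whether the window runs before as well as after activation. Where the setting is available in commercial uploads, also classify it as at or below versus above the TS threshold in force. Cross-tabulate both with the agreement groups.
3. Show later fingersticks taken during an active suspension separately, because glucose may have recovered or been treated by then.
4. Report the result as the share of fingerstick-checked suspensions with glucose not low, not as a false-suspension rate. Note that values near the threshold reflect ordinary measurement error.

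The cost is wording in two documents and one extra table. The sponsor must confirm that the threshold setting is available in commercial uploads: it is a listed summary item for the trial (SAP 7.2.4.4) but not in SAP 7.8. The ≤70 versus >70 split does not need it. The downside is that the share of suspensions confirmed as low may look less favourable than the agreement figure.
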